^m Spirometry may be performed pre- or post-bronchodilator at the Screening Visit. Spirometry will be performed pre-bronchodilator, before the morning dose of study drugs, and should be performed at approximately the same time at every visit. On the Day 1 and 15 Visits, spirometry will also be performed pre-bronchodilator, 5 hours (± 1 hour) after study drug administration.

ⁿ The ppFEV₁ assessment that will be used for stratification of randomization can be done any time during the Screening Period. See Section 9.1.2.2 of the protocol.

^o *CFTR* genotyping will be performed for all subjects. If the screening *CFTR* genotype result is not received before randomization, a previous *CFTR* genotype laboratory report may be used to establish eligibility. However, as outlined in Section 9.9 of the protocol, subjects who have been randomized and whose screening *CFTR* genotype does not confirm study eligibility must be discontinued from the study, even if a previous *CFTR* genotype laboratory report was used to establish eligibility.

^p FSH will be measured for any potential postmenopausal female subjects with at least 12 months of continuous spontaneous amenorrhea.

^q Blood samples will be collected for the G6PD activity test.

Table 11-3 Study VX16-445-001: Schedule of Assessments for Part F (if Conducted)

Event/Assessment ^a	Screening	Treatment Period: Period 1				ETT Visit ^b	Safety Follow-up 28 (± 7) Days After Last Dose
	Days -28 to -1	Day 1 ^c	Day 8 ^d (± 1 day)	Day 15 (± 2 days)	Day 29 (± 2 days)		
[REDACTED]							
Serum chemistry and hematology ^e	X	X	X	X	X	X	X
Coagulation ^g	X	X		X	X	X	X
PK sampling ^s		X		X	X	X	
VX-445/TEZ/VX-561 or placebo dosing ^t		Day 1 through Day 29					
AEs, medications ^u , treatments, and procedures	Continuous from signing of the ICF through the Safety Follow-up Visit						

AE: adverse event; CF: cystic fibrosis; CFQ-R: Cystic Fibrosis Questionnaire-Revised; *CFTR*: CF transmembrane conductance regulator gene; [REDACTED]; ECG: electrocardiogram; ETT: early termination of treatment; FSH: follicle-stimulating hormone; G6PD: glucose-6-phosphate dehydrogenase; ICF: informed consent form; IVA: ivacaftor; PE: physical examination; PK: pharmacokinetic; ppFEV₁: percent predicted forced expiratory volume in 1 second ; TEZ: tezacaftor

[REDACTED]

Blood samples will be collected for PK analysis of VX-445, TEZ, M1-TEZ, and VX-561. On the Day 1 Visit, samples will be collected before dosing (0 hours) and at 1, 2, 4, and 6 hours after dosing (relative to the morning dose). On the Day 15 Visit, samples will be collected before dosing (0 hours) and at 1, 2, 4, 6, and 8 hours after dosing. On the Day 29 Visit, a predose sample will be collected before the morning dose of study drug. At the ETT visit, a single blood sample for PK analysis will be collected.

^t On days of scheduled visits, the in-clinic dose of study drugs will be given in the morning, at least 6 hours apart from any other scheduled dose and after all predose assessments are complete. The last dose of VX-445/TEZ/VX-561 or placebo will be the morning dose on the Day 29 Visit. See Section 9.6.2 of the protocol for additional information about study drug administration.

^u Refer to Section 9.5.2 of the protocol for details.

[REDACTED]

Appendix B: Analysis Visit Windows for Safety and Efficacy Assessments

Table 11-4 Analysis Visit Windows for Safety and Efficacy Assessments			
Assessment	Visit^a	Target Study Day^b	Analysis Visit Window (in study days)
Safety Assessment (Parts D1 and D2)			
Serum Chemistry Hematology Weight	Day 1 (Baseline)	1	≤1 Pre-dose
	Day 8 (Part D1)	8	[1, 12] Day 1 post dose
	Day 15(Part D1)	15	(12, 22]
	Day 15(Part D2)	15	[1, 22] Day 1 post dose
	Day 29	29	(22, 47]
	Safety Follow-up	64	Use nominal visit
Coagulation	Day 1 (Baseline)	1	≤1 Pre-dose
	Day 15	15	[1, 22] Day 1 post dose
	Day 29	29	(22, 47]
	Safety Follow-up	64	Use nominal visit
Vital Signs Pulse Oximetry	Day 1 (Baseline)	1	≤1 Pre-dose
	Day 8 (Part D1)	8	[1, 12]
	Day 15(Part D1)	15	(12,22]
	Day 15(Part D2)	15	[1, 22]
	Day 29	29	(22, 33]
	Period 2 visit	Period 2 visit (36)	(33, 50]
	Safety Follow-up	64	Use nominal visit
Standard 12-Lead ECG	Day 1 (Baseline; before dosing)	1	Use nominal visit for all visits
	Day 1 (5 hours after dosing)	1	
	Day 8 (Part D1 only)	8	
	Day 15 (before dosing and 5 hours after dosing)	15	
	Day 29	29	
	Safety Follow-up	64	
Spirometry	Day 1 (5 hours post dose)	1	Use nominal visit
	Day 15 (5 hours post dose)	15	Use nominal visit
Safety Assessment (Part E)			
Serum Chemistry Hematology Vital Signs (including Weight) Pulse Oximetry	Day 1 (Baseline)	1	≤1 Pre-dose
	Day 15	15	[1, 22] Day 1 post dose
	Day 29	29	(22, 36]
	Day 43	43	(36, 50]
	Day 57	57	(50, 71]
	Safety Follow-up	85	Use nominal visit

^a Visit name is used to report data in tables, listings and figures.

^b Target day time point per protocol is predose, except for ECG and Spirometry measurements.

Table 11-4 Analysis Visit Windows for Safety and Efficacy Assessments			
Assessment	Visit^a	Target Study Day^b	Analysis Visit Window (in study days)
Coagulation	Day 1 (Baseline) Day 15 Day 29 Safety Follow-up	1 15 29 85	≤1 Pre-dose [1,22] Day 1 post dose (22, 57] Use nominal visit
Standard 12-Lead ECG	Day 1 (Baseline; before dosing) Day 1 (5 hours after dosing) Day 15 (before dosing and 5 hours after dosing) Day 29 Day 43 Day 57 Safety Follow-up	1 1 15 29 43 57 85	Use nominal visit for all visits
Spirometry	Day 1 (5 hours post dose) Day 15 (5 hours post dose)	1 15	Use nominal visit Use nominal visit
Safety Assessment (Part F)			
Serum Chemistry Hematology	Day 1 (Baseline) Day 8 Day 15 Day 29 Safety Follow-up	1 8 15 29 57	≤1 Pre-dose [1, 12] Day 1 post dose (12,22] (22, 43] Use nominal visit
Coagulation Vital Signs (including Weight) Pulse oximetry	Day 1 (Baseline) Day 15 Day 29 Safety Follow-up	1 15 29 57	≤1 Pre-dose [1,22] (22, 43] Use nominal visit
Standard 12-Lead ECG	Day 1 (Baseline; before dosing) Day 1 (5 hours after dosing) Day 15 (before dosing and 5 hours after dosing) Day 29 Safety Follow-up	1 1 15 29 57	Use nominal visit for all visits
Spirometry	Day 1 (5 hours post dose) Day 15 (5 hours post dose)	1 15	Use nominal visit Use nominal visit
Efficacy Assessment (Parts D1 and D2)			
Spirometry Sweat Chloride	Day 1 (Baseline) Day 8 (Part D1) Day 15 (Part D1) Day 15 (Part D2) Day 29 Period 2 visit Safety Follow-up	1 8 15 15 29 Period 2 visit (36) 64	≤1 Pre-dose (1, 12] (12, 22] (1, 22] (22, 33] (33, 50] Use nominal visit
CFQR	Day 1 (Baseline) Day 15 Day 29	1 15 29	≤1 Pre-dose (1, 22] (22, 47]
Efficacy Assessment (Part E)			

Table 11-4 Analysis Visit Windows for Safety and Efficacy Assessments			
Assessment	Visit^a	Target Study Day^b	Analysis Visit Window (in study days)
Spirometry	Day 1 (Baseline)	1	≤1 Pre-dose
	Day 15	15	(1,22]
	Day 29	29	(22, 36]
	Day 43	43	(36, 50]
	Day 57	57	(50, 71]
	Safety Follow-up	85	Use nominal visit
Sweat Chloride	Day 1 (Baseline)	1	≤1 Pre-dose
	Day 15	15	(1,22]
	Day 29	29	(22, 36]
	Day 43	43	(36, 50]
	Day 57	57	(50, 71]
CFQR	Day 1 (Baseline)	1	≤1 Pre-dose
	Day 15	15	(1,22]
	Day 29	29	(22, 43]
	Day 57	57	(43, 71]
Efficacy Assessment (Part F)			
Spirometry Sweat Chloride	Day 1 (Baseline)	1	≤1 Pre-dose
	Day 15	15	(1,22]
	Day 29	29	(22, 43]
	Safety Follow-up	57	Use nominal visit
CFQR	Day 1 (Baseline)	1	≤1 Pre-dose
	Day 15	15	(1,22]
	Day 29	29	(22, 43]

Notes:
 
The analysis visit windows will be applied using the following rules for both scheduled and unscheduled visits:
 
 1. If no numerical measurement is available within a visit window, the measurement will be considered missing for the visit. 2. If there is more than 1 numerical measurement available within the same visit window, use the following rules: 
 a. For efficacy parameters: if there are multiple measurements within a visit window, the measurement at the scheduled visit will be used. Otherwise, 
 i. If there are no measurements at the scheduled visit, then the measurement closest to the target day will be used; or ii. If there are multiple measurements with the same distance to the target day, the latest measurement will be used. b. For safety parameters: if there are multiple measurements within a visit window, 
 i. The measurement closest to the target day will be used; or ii. If there are multiple measurements within the same distance from the target day, the latest measurement will be used. iii. For tables of extreme lab measurements based on ULN or LLN, convert the lab measurements into times of ULN or LLN first, and then select the extreme measurement. 			

Derived Variables
 
 1. Age (in years) at first dose date 
Obtain age at screening (in days) in yy mm format (e.g., 24 years, 6 months) from screening vital signs page, and add 0.5 month to convert to days.
			

Table 11-4 Analysis Visit Windows for Safety and Efficacy Assessments			
Assessment	Visit^a	Target Study Day^b	Analysis Visit Window (in study days)

Obtain screening date from Date of Visit (DOV) page.
 
Then age (in years) at first dose date = integer part of $\{[(\text{first dose date} - \text{screening date}) \text{ in days} + \text{age at screening (in days)}] / 365.25\}$.
 
Correspondingly, age (in months) at first dose date = integer part of $12 * \{[(\text{first dose date} - \text{screening date}) \text{ in days} + \text{age at screening (in days)}] / 365.25\}$.
 
2. Age (in years) at post-baseline visit (for use in calculation of percent predicted spirometry variables)
 
Age (in years) at post-baseline visit = $[(\text{post-baseline visit date} - \text{screening date}) \text{ in days} + \text{age at screening (in days)}] / 365.25$
 
3. Missing First Dose Date or Last Dose Date
 
If the first dose date is missing, use Day 1 visit date.
 
If the last dose date is missing at final analysis, use maximum of Early Treatment Termination (ETT) visit date and last study drug administration date from EX SDTM domain (excluding PK dosing dates). When a subject is lost to follow up without ETT, impute the last dose date as the last treatment period visit date.
 
4. Missing Date for Drug Interruption
 
If the dates for drug interruption are completely missing or partially missing and cannot be determine in which period the interruption occurred, then assume the interruption occurred during the Period 1 for 1 day.
 
5. Sweat Chloride:
 
The qualified left arm and right arm sweat chloride assessments on Day 1 with the end date/time for a given arm up to 30 minutes after first dose time will be considered for baseline. If Day 1 value is unavailable or invalid, screening value will qualify as baseline.
			

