9.1.2.3 Run-in Period (Part E)

The Run-in Period of Part E is 4 weeks and is designed to establish a reliable on-treatment (TEZ/IVA) baseline for the Treatment Period (Period 1). Subjects will receive TEZ 100 mg qd/IVA 150 mg q12h during the Run-in Period. The first dose of TEZ/IVA will be administered at the Day -28 Visit. The last dose of TEZ/IVA within the Run-in Period will be administered on Day -1 (1 day before the Day 1 Visit).

Study eligibility for Part E subjects will be confirmed before the first dose of TEZ/IVA in the Run-in Period (on the Day -28 Visit). Subjects who prematurely discontinue TEZ/IVA during the Run-in Period will not be randomized or participate in the Treatment Period (Period 1), unless they rescreen and complete a 4-week Run-in Period ([Section 9.1.2.1.2](#)).

Study visits during the Run-in Period will occur as shown in [Table 3-7](#).

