A VX-561 dose of 150 mg qd was selected for evaluation in Part F based on preliminary PK results from a relative bioavailability study (Study VX16-770-018) evaluating the 50-mg tablet formulation of VX-561. 150-mg qd is predicted to result in similar PK parameters as IVA when administered alone at a dose of 150 mg q12h, including AUC_{0-24h} and C_{trough} . The VX-561 dose selection accounts for differences in the PK profile relative to IVA. VX-561 has been dosed up to 225 mg qd for 7 days in a Phase 1 study.

Treatment Duration

The 4-week treatment duration for the TC is based on previous experience with CF correctors and potentiators in clinical studies of subjects with CF. In previous studies of TEZ and IVA, PD effects were observed within 4 weeks of treatment. In Study VX06-770-101, treatment with IVA for 4 weeks resulted in statistically significant within-group changes from baseline in $ppFEV_1$ as well as a trend toward clinically meaningful improvements in the respiratory domain of the CFQ-R; differences in biomarkers of CFTR activity (sweat chloride) between IVA and placebo groups were also demonstrated. Furthermore, in Study VX11-661-101 dose-dependent improvements in lung function were observed for TEZ/IVA after 4 weeks of treatment, with the 2 highest dose groups showing statistically significant improvement in lung function versus placebo.¹⁷ In both studies, improvements in sweat chloride and $ppFEV_1$ were observed during the first week of dosing, with most of the effect observed within 14 days. Given the increased in vitro response of the TC relative to TEZ/IVA, it is expected that the 4-week treatment duration

of VX-445 will be sufficient to observe differences between treatment arms with respect to efficacy and PD endpoints.

Administration of VX-445, TEZ, IVA, and VX-561 With Food

Oral doses of VX-445, TEZ, IVA, and VX-561 will be administered under fed conditions. This is consistent with how VX-445, TEZ, IVA, and VX-561 were administered in nonclinical studies, including the GLP toxicity studies. Only a mild food effect is predicted for VX-445 oral absorption.

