8 STATISTICAL ANALYSIS

8.1 General Considerations

The analysis will be performed for each part, and presented by treatment group and overall, for the Treatment Period, unless specified otherwise. The treatment groups are defined as follows:

- Part D: F508del/MF genotypes group
 - Placebo, TC-low, TC-mid, and TC-high. The pooled TC-mid groups and the pooled placebo groups from Parts D1 and D2 will be used in all efficacy, pharmacodynamic (PD) and safety analyses for Part D.
- Part E: F508del/F508del genotype group
 - TEZ/IVA and TC-high.
- Part F: F508del/MF genotypes group
 - Placebo and TC2-high.

The Schedule of Assessments is provided in [Appendix A](#). The precision standards for reporting safety and efficacy variables are provided in an internal Biometrics document that specifies the programming rules including the precision for derived variables.

All individual subject data for those randomized or dosed with any amount of study drug will be presented in data listings.

Continuous variables will be summarized using the following descriptive summary statistics: the number of subjects (n), mean, SD, standard error (SE), median, minimum value (min), and maximum value (max). SE may not be reported for safety summary tables.

Categorical variables will be summarized using counts and percentages. Percentages will be presented to 1 decimal place.

Baseline value, unless otherwise specified, will be defined as the most recent non-missing measurement (scheduled or unscheduled) collected before the first dose of study drug on Day 1 of the Treatment Period. For ECG, baseline will be defined as the most recent non-missing measurement (or the average of triplicate measurements, if the most recent non-missing

measurement is obtained in triplicate), before the first dose of study drug on Day 1 of the Treatment Period.

Absolute change from baseline will be calculated as postbaseline value – baseline value.

Relative change from baseline will be calculated as (postbaseline value – baseline value)/baseline value.

Treatment-emergent (TE) period for Parts D and F will include the time from the first dose of study drug in the Treatment Period until 28 days after the last dose of study drug or end of study date (based on end of follow-up visit in CRFs), whichever occurs first.

For Part E, the TE period will be defined separately for the Run-In Period, and the Treatment Period:

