8.3.5.2.1 Parts D, E and F

The analysis of the absolute change in sweat chloride from baseline through Day 29 will be based on an MMRM model similar to the analysis of the primary efficacy variable for Parts D, E, and F, with the continuous baseline sweat chloride and continuous baseline ppFEV₁ as covariates. The presentation of results will also be similar.

The adjusted mean (with 95% CI) obtained from the MMRM analysis at each post-baseline visit through Day 29 in the Period 1 will be plotted by treatment group, for each part.

A waterfall plot showing the subject-level absolute change in sweat chloride at Day 29 will be presented, by treatment group for each part.

In addition, for each part, descriptive analyses of the change from baseline will be performed for all treatment groups by post-baseline visit.

8.3.5.3 Supportive Analysis for Absolute Change from Baseline in Sweat Chloride from Baseline through Day 29

Part D: Period 2

The Period 2 in Part D after Day 29 through Period 2 visit will be used to assess the washout effect of VX-445 on sweat chloride during the 1-week Period 2. This analysis will be based on fitting an Analysis of Covariance (ANCOVA) model to the absolute change from baseline in sweat chloride in the Period 2, using the group as a fixed effect, with the continuous baseline sweat chloride and baseline ppFEV₁ as covariates in the ANCOVA model. Groups will be assigned to placebo, TC-low, pooled TC-mid and TC-high the 4 randomized groups in the Period 1, will be assigned within each subject.

The adjusted mean of the change from baseline for placebo, TC-low, pooled TC-mid and TC-high at the Period 2 visit will be provided along with the corresponding *p*-value.

The adjusted mean (with 95% CI) obtained from the ANCOVA analysis at Period 2 visit will be plotted by randomized group, will be combined with the corresponding plot for the Period 1 from the primary analysis of sweat chloride.

Part E: Washout Period

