- ^b If the subject prematurely discontinues study treatment, an ETT Visit should be scheduled as soon as possible after the decision to terminate study drug treatment. Subjects who prematurely discontinue treatment will also be required to complete the Safety Follow-up Visit. If the ETT Visit occurs 3 weeks or later following the last dose of study drug, the ETT Visit will replace the Safety Follow-up Visit, and a separate Safety Follow-up Visit will not be required.
- ^c Part E subjects who meet criteria specified in Section 9.1.2.6 of the protocol will not have a Safety Follow-up Visit.
- ^d The Day -14 Visit is only required for subjects who are not transitioning directly from at least 14 days of uninterrupted TEZ/IVA treatment. Assessments at this visit may be performed postdose.
- ^e To be eligible to continue into the Treatment Period, subjects must have stable CF disease and have remained on stable CF medication regimen during the 28 days before the Day 1 Visit AND must not have had an acute non-CF illness within 14 days before the Day 1 Visit. See Section 9.1.2.4 of the protocol.
- ^f Randomization may occur on the previous day (Day -1 Visit) after all inclusion and exclusion criteria and criteria for entry into the Treatment Period have been confirmed. See Section 9.1.2.2.2 of the protocol.
- ^g CFQ-R must be completed before the start of any other assessments scheduled at that visit.
- ^h The predose assessment on the Day 1 Visit may be performed on the previous day (Day -1 Visit) if randomization has occurred.
- ⁱ Weight and height will be measured with shoes off.
- ^j Vital signs and pulse oximetry will be collected after the subject has been seated for at least 5 minutes.

Table 11-2 Study VX16-445-001: Schedule of Assessments for Part E

Event/Assessment ^a	Screening	Run-in Period		Treatment Period: Period 1			Washout Period		ETT Visit ^b	Safety Follow-up 28 (± 7) Days After Last Dose ^c
	Days -56 to -29	Day -28 (± 1 day)	Day -14 ^d (+ 13 days)	Day 1 ^e	Day 15 (± 2 days)	Day 29 (± 2 days)	Day 43 (± 3 days)	Day 57 (± 3 days)		
Standard 12-lead ECG ¹	X	X		X	X	X	X	X	X	X
Sweat chloride ^{h,m}	X		X	X	X	X	X	X	X	
Spirometry ⁿ	X ^o		X ^o	X	X	X	X	X	X	X
Urinalysis ^h	X	X		X	X	X	X	X	X	X
Pregnancy test (all females of childbearing potential)	Serum	Urine		Urine		Urine		Urine	Serum	Serum
CFTR genotype ^p	X									
FSH ^q	X									

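### In Part E, the sweat-chloride fallback baseline for subjects not coming directly from TEZ/IVA is a value from before the run-in, although an on-TEZ/IVA sample is scheduled at Day -14

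*SAP*

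**What the plan says.** SAP Appendix B, Derived Variables, item 5 accepts a Day 1 sweat-chloride collection that ends up to 30 minutes after the first dose, and then adds: "If Day 1 value is unavailable or invalid, screening value will qualify as baseline". No part is exempted.

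The general rule in SAP 8.1 differs. Its definition of baseline reads: "unless otherwise specified, will be defined as the most recent non-missing measurement (scheduled or unscheduled) collected before the first dose of study drug". In Table 11-4 the Part E sweat-chloride baseline window is any pre-dose value up to Day 1. Note 2a(i) to that table says: "If there are no measurements at the scheduled visit, then the measurement closest to the target day will be used".

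Protocol 9.1.2.3 describes the Part E run-in as "designed to establish a reliable on-treatment (TEZ/IVA) baseline for the Treatment Period (Period 1"). It also says: "The first dose of TEZ/IVA will be administered at the Day -28 Visit". The Part E schedule (Protocol Table 3-7, SAP Table 11-2) puts screening at Days -56 to -29 and lists sweat chloride at screening, Day -14 and Day 1, but not at Day -28. Footnote d limits the Day -14 sample to one group: "The Day -14 Visit is only required for subjects who are not transitioning directly from at least 14 days of uninterrupted TEZ/IVA treatment".

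The baseline feeds SAP 8.3.5.2.1: "The analysis of the absolute change in sweat chloride from baseline through Day 29 will be based on an MMRM model", with baseline sweat chloride and baseline ppFEV1 as covariates. It also feeds the Part E washout analysis in SAP 8.3.5.3.

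**The concern.** The run-in exists so that Period 1 change is measured from a state of TEZ/IVA treatment. Item 5 selects the one scheduled pre-dose sample that lies outside that state and skips the one inside it.

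Take a subject who was on no modulator at screening and has no valid Day 1 value. The TEZ/IVA effect gained during the run-in would be counted as part of the Period 1 fall. In the TEZ/IVA arm, a fall would appear although treatment had not changed. The same shift enters the baseline covariate and the washout comparison. SAP 8.3.5.2.1 follows the presentation of the primary analysis, which includes within-treatment estimates with p-values, so the distortion would reach reported results.

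A softer reading is that the screening value is merely eligible to serve as baseline. The text then still does not mention Day -14, and two programmers could derive different baselines from the same data.

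**Working it through.** **1. Timing**, relative to the first run-in dose at nominal Day -28:

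| Sample | Study days | Relative to first run-in dose |
|---|---|---|
| Screening (named by item 5) | -56 to -29 | 28 to 1 days before |
| Day -14 Visit (+13 days) | -14 to -1 | 14 to 27 days after |

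Protocol 9.3.2.2 reports that in the earlier IVA and TEZ/IVA studies, improvements in sweat chloride and ppFEV1 "were observed during the first week of dosing, with most of the effect observed within 14 days". The Day -14 sample should therefore carry most of the run-in effect, and the screening sample none of the effect of the run-in doses.

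**2. Can the screening value mean Day -14?** No. The documents treat the two as separate visits. The Part E ppFEV1 stratification rule (Protocol 9.1.2.2.1, SAP 8.2.2) uses the Screening Visit for directly transitioning subjects and the Day -14 Visit for all others. The plan thus already makes this distinction for ppFEV1 in the same subjects.

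**3. Which rule governs?** With Day 1 missing and Day -14 valid, SAP 8.1 (most recent) and note 2a(i) (closest to target day) both select Day -14. Item 5 selects screening. SAP 8.1 gives way where something else is specified, and item 5 specifies something else.

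**4. Who is affected?** Only non-transitioning subjects with no valid Day 1 value. Directly transitioning subjects, such as those from Study 661-110, are screened while on TEZ/IVA, so screening is an acceptable fallback for them.

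**5. Size per affected subject.** Let R be the screening value minus the on-TEZ/IVA value. The documents give no R; 5 to 15 mmol/L is assumed. Planned arm sizes are 18 and 6. The unadjusted mean change becomes more negative by R/n:

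| R (mmol/L) | TC-high, R/18 | TEZ/IVA, R/6 |
|---|---|---|
| 5 | 0.28 | 0.83 |
| 10 | 0.56 | 1.67 |
| 15 | 0.83 | 2.50 |

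**6. Effect of covariate adjustment.** The planned model evaluates adjusted means at the pooled baseline mean. Let β, taken between 0 and 1 and held fixed, be the slope of the post-baseline value on baseline, and suppose all 24 subjects contribute. One affected subject raises the arm's baseline mean by R/n and the pooled mean by R/24. The arm's adjusted mean change then falls by R/n - (1-β)(R/n - R/24):

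- TEZ/IVA: R[1/6 - (1-β)/8], which runs from R/24 (β = 0) to R/6 (β = 1). At R = 15 this is 0.63 to 2.50 mmol/L, and at β = 0.5 it is 15 × (0.1667 - 0.0625) = 1.56.
- TC-high: R[1/18 - (1-β)/72], which runs from R/24 to R/18. At R = 15 this is 0.63 to 0.83 mmol/L.

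The unadjusted figures in step 5 are therefore upper limits for the adjusted within-group shift under this simplification.

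**The case against.** **The general rules already give the right answer.** Protocol 12.3.1, SAP 8.1, the Table 11-4 window and note 2a(i) all point to Day -14. SAP 2.1 lists only two modifications to the protocol, and a changed sweat-chloride baseline is not one of them. On that record item 5 could be read as making screening eligible, with 8.1 choosing among eligible values. This is a fair reading but not the only one, because both general definitions yield to specific ones. Under either reading the text needs an edit.

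**The trigger is rare.** A valid screening sample is required for entry (Protocol 8.2.1, criterion 5), one valid arm is enough (SAP 8.3.5), the Day 1 sample may be taken on Day -1 once the subject is randomised, and item 5 allows 30 minutes after first dose. This stands. However, SAP 8.3.5 sets volumes under 15 µL and values outside 10 to 160 mmol/L to missing, so invalid Day 1 results are foreseen.

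**The Day -14 sample is imperfect.** Footnote d lets its assessments be done after dosing, whereas the other Part E samples are pre-dose by default. This is a real but small mismatch, and it does not make a value from before the run-in preferable.

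**Screening is not always free of modulators.** Part E bars other CFTR modulators only from Day -28 (Protocol Table 9-5), and the non-transitioning group includes subjects with interrupted or short TEZ/IVA use. The size and even the sign of R are then uncertain. This stands, and it is why the argument about a spurious fall is limited to subjects on no modulator at screening.

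**Conclusion.** The concern holds. Followed as written, item 5 gives non-transitioning Part E subjects with no valid Day 1 value a baseline from before the run-in, against the run-in's stated purpose and the SAP's own default, while a scheduled on-TEZ/IVA value goes unused.

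The consequence is limited. One affected subject shifts the unadjusted mean change by 0.28 to 0.83 mmol/L in TC-high or 0.83 to 2.50 mmol/L in TEZ/IVA, on an assumed R of 5 to 15 mmol/L and the planned arm sizes; baseline adjustment would lessen this. The documents give neither the failure rate at Day 1 nor the share of non-transitioning subjects, so no count is claimed, and it may be zero. The difference between arms is disturbed only by chance imbalance in affected subjects, not by systematic bias. Sweat chloride is a secondary endpoint. The primary ppFEV1 analysis and the Part D dose-response test are unaffected. The point should be corrected because the rule is wrong for this group and the correction is almost free, not because the results are likely to turn on it.

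**What to change.** In SAP Appendix B, Derived Variables, item 5, replace the screening fallback with this rule: where no valid Day 1 value exists, baseline is the latest valid sweat-chloride result from any visit, scheduled or not, preceding the first Period 1 dose. Leave the 30-minute Day 1 allowance as it is.

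In Part E the Day -14 value then takes precedence over screening where it exists. Screening remains the fallback for directly transitioning subjects, for anyone with no valid later value, and in Parts D and F. It would help to state in the same clause that a Day -14 sample taken after dosing is acceptable for this purpose.

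The cost is one clause, using data already scheduled. No subject is lost from the sweat-chloride model. The change should be made before the Part E data are unblinded, so that the baseline is not chosen with results in view.
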